### **9.3.3.1 Study Safety Evaluation Criteria**

If any of the following events occur in a subject in the study who has received BMN 270 infusion, an urgent evaluation by the DMC will be required and further enrollment into the trial will be temporarily put on hold if recommended by the DMC per Section 9.1.

1. Liver dysfunction (criteria do not apply to ALT elevations with an extra-hepatic etiology):
  - o ALT > 5x ULN, for more than 2 weeks
  - o ALT > 3x ULN **and** (total bilirubin >2x ULN **or** INR >1.5)
  - o ALT > 3x ULN with signs and symptoms of liver dysfunction
2. The occurrence of Grade 4 or Grade 5 adverse events assessed as related to study drug (events of liver dysfunction are defined above).
3. The occurrence of an AE of hepatic failure.
4. The detection of high-titer neutralizing antibodies (>5 BU) to hFVIII following BMN 270 infusion in two subjects.
5. The occurrence of any cancer (except non-melanoma skin cancer) at any point after BMN 270 infusion.
6. The occurrence of a thromboembolic event with FVIII activity > 150 IU/dL in one subject.

If any of the following events occurs in a subject in the study who has received BMN 270 infusion, an urgent evaluation by the DMC will be required. Further enrollment into the trial will continue while DMC evaluation is ongoing, unless deemed otherwise by the DMC:

1. The detection of high-titer neutralizing antibodies (>5 BU) to hFVIII following BMN 270 infusion in one subject.
2. Occurrence of a thromboembolic event in one subject.

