#### **9.4.8.1 Concomitant Hemophilia Treatments**

Subjects on prophylactic FVIII therapy will discontinue their regular treatment regimen starting 4 weeks after the day of infusion and switch to an “on-demand” schedule. FVIII replacement therapy can always be taken as needed by the subject for treatment of an acute bleeding episode; the subject must carefully record his treatment and bleeding episodes in his diary. Prophylactic FVIII use can be used on a case-by-case basis and in consultation with the Medical Monitor to prevent bleeding in extenuating circumstances (eg, peri-operative).

In addition, information on FVIII usage and bleeding episodes by medical history must be well-documented and available and will be collected from subjects for the 12-month period immediately preceding study enrollment. Further information on the details that should be provided as part of the subject’s well-documented medical and FVIII usage history are provided in the On Site File Binder.

In order to enable rigorous comparisons of pre-study versus on-study FVIII usage and bleeding episodes, the Medical Monitor will review each screened patient’s prior bleed and hemophilia medication logs to determine if they are of "high-quality". Elements that will be assessed to judge the quality of such historical data may include, but are not limited to, the following:

- Date, type (eg, joint, muscle, other), location of bleeds
- Date, name, dose (calculated in IU/kg), and reason for use (eg, usual prophylaxis, one-time prophylaxis, treatment for bleed, surgery) of hemophilia medications.

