### **10.1.1.1 Bleeding and Suspected Bleeding Events**

All bleeding events and suspected bleeding events, regardless of the need for exogenous FVIII therapy as treatment, should be captured in subject diaries and recorded on the designated bleeding eCRF. Bleeding events and suspected bleeding events should not be reported as adverse events, with the following exception:

- All bleeding events and suspected bleeding events which meet one or more of the criteria for being serious (refer to Section 10.2) should be reported as serious adverse events (whether or not they are bleeding events that are normal sequelae of hemophilia, and whether or not they required exogenous FVIII as treatment).

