#### **10.3.3.2 Severity**

Severity (as in mild, moderate, or severe headache) is not equivalent to seriousness, which is based on subject/event outcome or action criteria usually associated with events that pose a threat to a subject's life or functioning. The Investigator will determine the severity of each AE, SAE and EOSI using the NCI CTCAE v4.03. Adverse events that do not have a corresponding CTCAE term will be assessed according to the general guidelines for grading used in the CTCAE v4.03 as stated in [Table 10.3.3.2.1](#).

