**Table 10.3.3.3.1: Causality Attribution Guidance**

Relationship	Description
Not Related	
 
Exposure to the IP has not occurred
 
 
OR
 
 
The administration of the IP and the occurrence of the AE are not reasonably related in time
 
 
OR
 
 
The AE is considered likely to be related to an etiology other than the use of the IP; that is, there are no facts, evidence, or arguments to suggest a causal relationship to the IP.
 

Related	
 
The administration of the IP and the occurrence of the AE are reasonably related in time
 
 
AND
 
 
The AE could possibly be explained by factors or causes other than exposure to the IP
 
 
OR
 
 
The administration of IP and the occurrence of the AE are reasonably related in time
 
 
AND
 
 
The AE is more likely explained by exposure to the IP than by other factors or causes.
 

Factors suggestive of a causal relationship could include (but are not limited to):

- Plausible temporal relationship
- Absence of alternative explanations
- Rarity of event in a given patient or disease state
- Absence of event prior to study drug exposure
- Consistency with study product pharmacology
- Known relationship to underlying mechanism of study drug action
- Similarity to adverse reactions seen with related drug products
- Abatement of AE with discontinuation of study drug, and/or recurrence of AE with reintroduction of study drug

The Investigator's assessment of causality for individual AE reports is part of the study documentation process. Regardless of the Investigator's assessment of causality for

---

individual AE reports, the Sponsor will promptly evaluate all reported SAEs against cumulative product experience to identify and expeditiously communicate possible new safety findings to Investigators and applicable regulatory authorities.

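### A life-threatening or fatal bleed after the Week 4 stop of prophylaxis gets mandatory urgent DMC review only if it is judged related to study drug, because no trigger in Protocol 9.3.3.1 names bleeding

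*Protocol*

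**What the plan says.** Protocol 9.3.3.1 has two lists of events that require urgent DMC evaluation. Under the first (6 items), enrollment is put on hold if the DMC recommends it. Under the second (2 items), enrollment continues unless the DMC decides otherwise. Item 2 of the first list is "The occurrence of Grade 4 or Grade 5 adverse events assessed as related to study drug". Other items have no such qualifier, for example "The occurrence of any cancer (except non-melanoma skin cancer) at any point after BMN 270 infusion" in the first list and "Occurrence of a thromboembolic event in one subject" in the second.

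On prophylaxis, Section 9.4.8.1 states: "Subjects on prophylactic FVIII therapy will discontinue their regular treatment regimen starting 4 weeks after the day of infusion". Subjects then treat on demand.

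Under Section 10.1.1.1, bleeds are not reported as adverse events unless they are serious. Serious bleeds "should be reported as serious adverse events (whether or not they are bleeding events that are normal sequelae of hemophilia", whether or not FVIII was needed. On grading, Section 10.3.3.2 says: "The Investigator will determine the severity of each AE, SAE and EOSI using the NCI CTCAE v4.03". Section 10.3.3.3 has the investigator determine relationship to study drug, guided by Table 10.3.3.3.1.

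**The concern.** The protocol itself creates a period in which a subject may be under-protected: prophylaxis stops on a calendar date, and the visible text of Sections 9.1 and 9.4.8.1 sets no FVIII level that must be reached first. The protocol expects that some subjects may respond poorly. The Synopsis defines treatment failure as not reaching 5 IU/dL by Week 52, or as being unable to stay off prophylaxis because of joint bleeds. The study rationale also names the risk of death from intracranial hemorrhage.

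A life-threatening bleed in such a subject bears directly on benefit and risk at 4E13 vg/kg, and the DMC may recommend a different dose. Whether that bleed must go to the DMC urgently depends on a causality rating that asks only about the product. The table has no category for harm from withdrawn prophylaxis combined with inadequate expression. The same event could therefore receive mandatory urgent evaluation at one site and not at another.

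**Working it through.** No sample size, power or event-rate figure bears on this point. The check is a count of the triggers, followed by tracing a severe bleed through the safety sections.

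**Step 1. The triggers in 9.3.3.1.**

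| List, item | Event | Names bleeding? | Relatedness to study drug required? |
|---|---|---|---|
| 1, 1 | Liver dysfunction (three ALT-based criteria) | No | No (ALT rises of extra-hepatic origin are excluded) |
| 1, 2 | Grade 4 or 5 adverse event | No | **Yes** |
| 1, 3 | Hepatic failure | No | No |
| 1, 4 | FVIII inhibitor above 5 BU, two subjects | No | No |
| 1, 5 | Cancer other than non-melanoma skin cancer | No | No |
| 1, 6 | Thromboembolic event with FVIII above 150 IU/dL | No | No |
| 2, 1 | FVIII inhibitor above 5 BU, one subject | No | No |
| 2, 2 | Thromboembolic event, one subject | No | No |

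Total: 6 + 2 = 8. Items naming bleeding: 0 of 8. Items requiring relatedness: 1 of 8. Items without that requirement: 8 − 1 = 7.

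**Step 2. Can a severe bleed reach any trigger?** A life-threatening or fatal bleed is serious under Section 10.2, so Section 10.1.1.1 makes it an SAE. Table 10.3.3.2.1 likewise treats Grade 4 and 5 events as SAEs. It is therefore an adverse event that can meet item 2 of the first list. The other 7 items could be met only by a different event occurring alongside it, such as a high-titer inhibitor or hepatic failure.

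**Step 3. How would causality be rated?** Table 10.3.3.3.1 allows two readings of the same bleed:

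- *Related*, if reasonably related in time, even where "The AE could possibly be explained by factors or causes other than exposure to the IP". Item 2 is met and urgent DMC evaluation is mandatory.
- *Not Related*, if another etiology is considered likely, meaning that "there are no facts, evidence, or arguments to suggest a causal relationship to the IP". An investigator who attributes the bleed to underlying hemophilia can choose this. No trigger is then met.

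**Step 4. Does another provision make the urgent evaluation mandatory?**

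- Section 10.2.1: bleeding is not an event of special interest.
- Section 10.5.1: SAEs are reported within 24 hours, but to the sponsor's pharmacovigilance group.
- Section 10.3.3.3: the sponsor evaluates all SAEs whatever the investigator's causality rating, with no stated DMC step.
- Section 10.8: urgent safety measures are provided for, with no mandatory DMC evaluation.
- Section 15: the DMC reviews subject data on an ongoing basis, which is not an urgent review triggered by an event.
- Sections 9.1 and 9.7.3.1: after recurrent bleeds, the investigator and Medical Monitor discuss resuming prophylaxis.

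Each helps to detect or manage the event. None requires urgent DMC evaluation of a bleed rated Not Related.

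**The case against.** The strongest reply is that the Related definition is broad. Timing is enough even when other causes are possible, and in a low responder taken off prophylaxis because of the gene therapy there is an obvious argument for a link. Most such bleeds might therefore be rated Related. That is fair, and divergence between sites is a possibility under the text, not something shown to have happened. But the Not Related route through underlying disease remains open.

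Section 9.3.3.1 also does not say who makes the assessment, so a sponsor assessment might count. The text does not exclude this, but Section 10.3.3.3 and SAP 14.1 assign causality to the investigator, and nothing says that a sponsor view can meet the trigger instead.

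Bleeding is the disease under study and a secondary endpoint, so filtering background events by relatedness is a defensible choice, whereas cancer or thromboembolism would be a new harm. This explains the contrast but does not justify it for Grade 4 or 5 bleeds after a stop that the protocol directs. Thromboembolism, a hazard of too much FVIII, triggers on one event whatever its cause; life-threatening bleeding, the hazard of too little, does not.

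Three limits stand. The DMC Charter is not available and may contain further triggers. Weekly FVIII assays through Week 36, on-demand FVIII and ongoing DMC review lower the risk and make it unlikely that the event would be missed. With one subject enrolled and enrollment terminated (SAP Sections 1 and 4), there is little left for a trigger to act on.

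**Conclusion.** The concern holds. On the protocol text, urgent DMC evaluation of a Grade 4 or 5 bleed after the Week 4 stop depends on the causality rating, because 0 of 8 triggers name bleeding and the single one that such a bleed can meet in itself requires relatedness. The gap is narrow: it concerns mandatory urgent review, not whether the event is reported or eventually seen. No event rate is claimed, because the documents give none.

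The conclusion assumes that the relatedness assessment is the investigator's, as Section 10.3.3.3 indicates, and that the redacted text sets no FVIII threshold for stopping prophylaxis. It speaks only to the protocol, since the Charter cannot be checked. For this study the practical effect is small. The wording should still be corrected in any further amendment or reuse of the section.

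**What to change.** Add one item to the second list in Protocol 9.3.3.1, where enrollment continues during the evaluation:

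*Occurrence of a Grade 4 or Grade 5 bleeding event after discontinuation of FVIII prophylaxis, regardless of causality.*

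The DMC keeps the decision on enrollment, and the rules on stopping or resuming prophylaxis do not change.

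The cost is one line of text. No new data field is needed, because serious bleeds are already reported as SAEs within 24 hours and every SAE is already graded. The downside is an occasional extra DMC evaluation, including for a rare purely traumatic bleed, which the DMC can close quickly.

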### **9.3.4 Subject Identification and Replacement of Subjects**

Each subject will be assigned a unique subject identifier. This unique identifier will be on all eCRF pages. In legal jurisdictions where use of initials is not permitted, a substitute identifier will be used.

Subjects who withdraw from the study after receiving BMN 270 will not be replaced.

### **9.3.5 Duration of Subject Participation**

The duration of participation for each subject will be approximately 264 weeks. This includes 4 weeks of screening, 1 day of BMN 270 infusion, 52 weeks of Post-Infusion Follow-Up, and 208 weeks of Long-Term Follow-Up.

## **9.4 Treatments**

### **9.4.1 Treatments Administered**

BioMarin and/or its designee will provide the study site with a supply of IP sufficient for the completion of the study. BioMarin is responsible for shipping study drug to clinical sites.

### **9.4.2 Identity of Investigational Product**

#### **9.4.2.1 Product Characteristics and Labeling**

The study drug is labelled according to the particulars approved by the relevant regulatory agencies.

### **9.4.3 Storage**

At the study site, all IP must be stored under the conditions specified in the Pharmacy Manual in a secure area accessible only to the designated pharmacists and clinical site personnel. All IP must be stored and inventoried and the inventories must be carefully and accurately documented according to applicable state, federal and local regulations, ICH GCP, and study procedures.

### **9.4.4 Directions for Administration**

On the day of infusion, the subject will come to the infusion site, where a physical examination will be performed by the Investigator or designee. If the subject is found to have an active acute illness at the time of planned infusion, then the infusion should be deferred until the illness has resolved; screening procedures may require repetition if outside the specified window. An IV catheter or butterfly needle will be inserted into a suitable peripheral vein (eg, the median cubital vein) and flushed with saline. FVIII replacement

therapy will not be given since venipuncture is a minimally invasive procedure in these individuals under ordinary conditions.

[REDACTED]

[REDACTED] Vital signs (pulse, blood pressure, respiration rate and temperature) should be monitored at 15 minute ( $\pm 5$  minutes) intervals throughout the time period of the infusion.

As with any infused biological product, there is a potential risk of acute, systemic hypersensitivity reactions (including anaphylaxis) with BMN 270. Dosing will be administered at a qualified infusion site, with appropriate resuscitation equipment and medication available and easily accessible.

Clinical staff administering BMN 270 should be trained appropriately in recognizing and managing the signs and symptoms associated with potential hypersensitivity, anaphylactic, and anaphylactoid reactions. Additionally, the Investigator should be familiar with Sampson's criteria for defining anaphylaxis (Sampson, 2006; Appendix 1).

Should symptoms of potential hypersensitivity occur, the infusion may be slowed or halted at the Investigator's discretion, with consideration of the subject's clinical condition. If the infusion is halted, it should only be restarted if the Investigator considers it safe and appropriate to do so. Antihistamines, anti-pyretic, and/or corticosteroid administration is permitted prior to restarting an interrupted infusion by an infusion-related reaction. At the restart, the infusion rate may be adjusted [REDACTED]

[REDACTED] with careful monitoring of the subject.

In case of hypersensitivity or adverse drug reaction, safety assessment, including physical examination and vital signs, will be done and additional blood samples will be collected [REDACTED]

In-patient observation can be extended and additional blood samples can be collected if deemed necessary at the discretion of the Investigator and Medical Monitor.

Following completion of the infusion, vital signs will be monitored hourly ( $\pm 5$  minutes). If the vital signs are stable the catheter will be removed 8 hours after the infusion. Hemostasis at the puncture site will be established by applying pressure according to standard protocol for infusing FVIII concentrates. Subjects will remain in the clinic for at least 8 hours to observe for any immediate toxicity of the procedure; in-patient observation can be extended beyond 8 hours if needed per Investigator discretion, or the subject may transfer to a separate facility based on the evaluation and judgment of the Principal Investigator after consultation with the Medical Monitor.

Prior to discharging subjects from the clinic, the Investigator or designee should instruct subjects how to recognize signs and symptoms of potential (delayed) hypersensitivity reactions and anaphylaxis, and to contact a medical practitioner or seek emergency care in case of such an event.

#### **9.4.5 Method of Assigning Subjects to Treatment Groups**

Subjects who meet all eligibility criteria (refer to Section 9.3.1 and Section 9.3.2) may be enrolled into the study. Approval by the Medical Monitor will be required prior to enrollment of each study subject. Upon their enrollment into the study, subjects will be assigned a unique subject number.

Approximately 40 subjects will be enrolled at 4E13 vg/kg.

#### **9.4.6 Selection of Dose Used in the Study**

Data from an ongoing first in human study (Clinical Study 270-201) indicates that following single escalated doses of BMN 270 (6E12, 2E13, 4E13, 6E13 vg/kg), dose-related increases in FVIII activity were observed, with concurrent improvements in bleeding episodes and exogenous FVIII utilization, particularly at the 4E13 and 6E13 vg/kg dose levels. At all dose levels, BMN 270 is considered to be well-tolerated with mild increases in ALT as the most common adverse event. Please refer to the IB for detailed efficacy and safety data.

In order to further evaluate the dose-response relationship of BMN 270, subjects will be enrolled at a dose of 4E13 vg/kg. This dose is expected to be safe and effective based on clinical experience to date in 270-201. The DMC will review emerging safety and efficacy data and may recommend that a different dose (not to exceed 6E13 vg/kg) be administered. In such a case, up to 40 additional subjects may be enrolled at the new dose.

#### **9.4.7 Blinding**

This is an open-label study.

#### **9.4.8 Prior and Concomitant Medications**

All prescription and over-the-counter medications (including dietary and herbal supplements) taken by a subject for 30 days before Screening will be recorded on the designated eCRF.

The Investigator may prescribe additional medications, deemed necessary to provide adequate prophylactic or supportive care, during the study, as long as the prescribed medication is not prohibited by the protocol. In the event of an emergency, any needed medications may be prescribed without prior approval, but the Medical Monitor must be notified of the use of any contraindicated medications immediately thereafter. Any concomitant medications added or discontinued during the study should be recorded on the eCRF. Medications should, whenever possible, not be recorded in the electronic database with a frequency of PRN.

The following medications are prohibited starting 30 days before Screening and through the end of the study, and the Sponsor must be notified if a subject receives any of these during the study:

- Any investigational therapy
- Systemic immunosuppressive agents, except for corticosteroids
- Emicizumab
- Fitusiran
- Concizumab
- Efavirenz
- Lamivudine

The following medications should be avoided, starting 30 days prior to and for at least 52 weeks after BMN 270 infusion and minimized throughout the remaining duration of the study.

- Alcohol
- Herbal and natural remedies and dietary supplements
- Medications which may be hepatotoxic

Vaccines should also be avoided during this period, but in particular during the first 26 weeks unless clinically indicated.

The following medications should be avoided during oral corticosteroid therapy:

- Vaccines
- NSAIDs

#### **9.4.8.1 Concomitant Hemophilia Treatments**

Subjects on prophylactic FVIII therapy will discontinue their regular treatment regimen starting 4 weeks after the day of infusion and switch to an “on-demand” schedule. FVIII replacement therapy can always be taken as needed by the subject for treatment of an acute bleeding episode; the subject must carefully record his treatment and bleeding episodes in his diary. Prophylactic FVIII use can be used on a case-by-case basis and in consultation with the Medical Monitor to prevent bleeding in extenuating circumstances (eg, peri-operative).

In addition, information on FVIII usage and bleeding episodes by medical history must be well-documented and available and will be collected from subjects for the 12-month period immediately preceding study enrollment. Further information on the details that should be provided as part of the subject’s well-documented medical and FVIII usage history are provided in the On Site File Binder.

In order to enable rigorous comparisons of pre-study versus on-study FVIII usage and bleeding episodes, the Medical Monitor will review each screened patient’s prior bleed and hemophilia medication logs to determine if they are of "high-quality". Elements that will be assessed to judge the quality of such historical data may include, but are not limited to, the following:

- Date, type (eg, joint, muscle, other), location of bleeds
- Date, name, dose (calculated in IU/kg), and reason for use (eg, usual prophylaxis, one-time prophylaxis, treatment for bleed, surgery) of hemophilia medications.

